2.2.3 Nivolumab Dose

The approved dose of nivolumab is 240 mg infused over 60 minutes every 2 weeks for NSCLC, unresectable or metastatic melanoma and advanced renal cell carcinoma (RCC). In this study, a flat dose of 360 mg nivolumab administered as an IV infusion over 30 minutes and a dosing schedule of every 3 weeks has been selected. Nivolumab has been shown to be safe and well tolerated up to a dose level of 10 mg/kg (Bristol-Myers Squibb, internal data). Population pharmacokinetic analyses have shown that the pharmacokinetics of nivolumab is linear with proportional exposure over a dose range of 0.1 to 10 mg/kg; no differences in pharmacokinetics across ethnicities and tumor types were observed. Using the population pharmacokinetic model developed, the exposures following administration of several dosing regimens of nivolumab administered as a flat dose were simulated, including 360 mg administered every 3 weeks. The simulated steady state average concentration following administration of nivolumab 360 mg every 3 weeks are expected to be similar to those following administration of nivolumab 240 mg every 2 weeks and 3 mg/kg every 2 weeks to subjects weighing 80 kg, the approximate median weight of subjects with NSCLC, unresectable or metastatic melanoma and RCC used in the population pharmacokinetic analyses. The steady state peak concentrations following nivolumab 360 mg every 3 weeks are predicted to be less than those following the administration of nivolumab 10 mg/kg every 2 weeks providing sufficient safety margins. Finally, nivolumab is being studied as nivolumab 360 mg combined with platinum-doublet chemotherapy administered every 3 weeks for the treatment of NSCLC in a Phase 3 study.

Previous clinical studies of nivolumab monotherapy have used a 60 minute infusion duration wherein, nivolumab has been safely administered up to 10 mg/kg over long treatment periods. Infusion reactions including high-grade hypersensitivity reactions have been uncommon across nivolumab clinical program. In CA209010, a dose association was observed for infusion site reactions and hypersensitivity reactions (1.7% at 0.3 mg/kg, 3.7% at 2 mg/kg and 18.5% at 10

mg/kg). All the events were Grade 1-2 and were manageable. An infusion duration of 30 minutes for nivolumab 360 mg is not expected to present any safety concerns compared to the prior experience at 10 mg/kg nivolumab dose infused over a 60 minute duration. The safety of nivolumab 3 mg/kg administered as a 30 minutes infusion was assessed in subjects (n=322) with previously treated advanced NSCLC. Overall, there were no clinically meaningful differences in the frequency of hypersensitivity/infusion-related reactions (of any cause or treatment-related) in subjects administered nivolumab over a 30 minutes infusion compared with that reported for subjects with the 60 minutes infusion. Thus, it was shown that nivolumab can be safely infused over 30 minutes.

3. Treatment of Subjects

3.1 Subject Enrollment and Treatment Administration

All subjects who sign a consent form will be assigned a unique Subject Identification Number. This number will be used to identify the subject throughout the study and must be used on all study documentation. Subjects will be considered enrolled after receiving any investigational product; consented subjects who do not receive investigational product will be considered screen failures.

The Apexigen Medical Monitor (or designee) will review the subject's information before enrollment. Only subjects who are approved by the Apexigen Medical Monitor (or designee) will be allowed to enroll in the study. During normal business days, a minimum of 24 hours will be required for the Apexigen Medical Monitor (or designee) to approve a subject for enrollment. Additional time may be required when approval is sought during a weekend or holiday.

Subject enrollment into a DL cohort of the Phase 1b dose-escalation or in the Phase 2 dose-expansion will follow the rules outlined in [Section 2.2](#).

On treatment days, nivolumab will be administered first, followed by APX005M.

During Phase 1b dose-escalation, in any of the multi-subject cohorts, the first two subjects must receive the first dose of investigational product at least 72 hours apart.

During the Phase 1b dose-escalation portion of the study all subjects will be monitored in the research clinic for 4 hours after the first 2 infusions of APX005M and as clinically indicated thereafter and during the Phase 2 dose-expansion portion of the study.

All subjects will be discharged from clinic after a clinical evaluation. Subjects should have stable vital signs including: lack of orthostatic hypotension (systolic blood pressure >100 mmHg, or no lower than 10 mm from baseline) without IV hydration (no hydration for at least 2 hours prior to discharge), lack of hypoxia (oxygen saturation >90% without oxygen), temperature <38°C, heart rate <110 beats/min.

After discharge, all subjects in Phase 1b should be monitored by a caregiver or by a healthcare professional for 24 hours after the first 2 infusions of APX005M and as clinically indicated thereafter. Subjects in the Phase 2 dose-expansion portion of the study should be monitored as clinically indicated.

3.2 Study Treatment

3.2.1 Investigational Products

An investigational product, also known as investigational medicinal product, is defined as follows:

A pharmaceutical form of an active substance or placebo being tested or used as a reference in a clinical study, including products already with a marketing authorization but used or assembled (formulated or packaged) in a different way than the authorized form, or used for an unauthorized indication, or when used to gain further information about the authorized form.

In this protocol, the investigational products are APX005M and nivolumab.

The Pharmacy Manual contains detailed information about packaging, labeling, storage, dispensing, preparation and administration of the infusion solutions of APX005M and nivolumab.

3.2.2 Non-Investigational Product

Any other medications used in the study as support or rescue medication for preventative, diagnostic, or therapeutic reasons, components of the standard of care for a given diagnosis, are considered non-investigational products.

3.3 Timing of Investigational Products Administration

Investigational products may be administered up to 3 days before or after the scheduled Day 1 in the case of medical / surgical events or logistical reasons not related to study therapy (e.g., elective surgery, unrelated medical events, patient vacation, and/or holidays); if retreatment criteria are met subjects should restart treatment within 12 weeks of last dose of investigational product unless otherwise discussed with Apexigen (or designee). Every effort should be made to maintain a 21-day dosing schedule. The reason for delay will be documented in the patient's study record.

3.3.1 Nivolumab

Nivolumab is administered on Day 1 of each 3-week treatment cycle as a dose of 360 mg using a 30-minute IV infusion. It is not to be administered as an IV push or bolus injection. Nivolumab injection can be infused undiluted (10 mg/mL) or diluted with 0.9% Sodium Chloride Injection,

USP or 5% Dextrose Injection, USP to protein concentrations as low as 1 mg/mL. Nivolumab injections should be administered through a 0.2-micron to 1.2-micron pore size, low-protein binding in-line filter and are compatible with polyvinyl chloride (PVC) or polyolefin containers and infusion sets, and glass bottles.

Sites should make every effort to target infusion timing to be as close to 30 minutes as possible. However, given the variability of infusion pumps from site to site, a window between -5 minutes and +10 minutes is permitted (i.e., infusion time is 25 minutes to 40 minutes). The nivolumab infusion can be interrupted in the case of infusion reaction (see [Section 3.4.1.2](#)). Once symptoms resolve, infusion should be restarted at 50% of the initial infusion rate (e.g., from 100 mL/hr to 50 mL/hr).

The Pharmacy Manual contains specific instructions for the preparation of the nivolumab infusion and administration of infusion solution.

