3.3.2 APX005M

APX005M is administered on Day 1 of each 3-week treatment cycle approximately 30 minutes following nivolumab using a 60 minute IV infusion. Sites should make every effort to target infusion timing to be as close to 60 minutes as possible. A window between -5 minutes and +10 minutes is permitted (i.e., infusion time is 55 minutes to 70 minutes).

The APX005M infusion can be interrupted in the case of infusion reaction (see [Section 3.4.1.2](#)). Once symptoms resolve, infusion should be restarted at 50% of the initial infusion rate (e.g., from 50 mL/hr to 25 mL/hr). A lower infusion rate may be considered for patients who experience repeated infusion reactions, after discussion with Apexigen Medical Monitor (or designee).

The Pharmacy Manual contains specific instructions for the preparation of the APX005M infusion and administration of infusion solution.

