 - **Grade 1-2:** symptomatic treatment (e.g. antihistamines, topical steroids). For persistent ($>1-2$ weeks) or recurrent symptoms consider skin biopsy and treatment delay.
 - **Grade 3-4:** consider skin biopsy and consult dermatologist. Treat with IV corticosteroids followed by oral corticosteroids until symptoms improve to Grade 1 or less.
- **Infusion Reaction/Cytokine Release Syndrome**

Precautions should be observed during the administration of APX005M and nivolumab. Emergency agents including oxygen, oral and endotracheal airways, intubation equipment epinephrine, antihistamines, and corticosteroids should be available and used if required at the Investigator's discretion.

Subjects should be instructed that symptoms associated with cytokine release syndrome/infusion reaction can occur within 48 hours following the administration of the APX005M or nivolumab, and if such symptoms develop while they are at home, they should contact the Investigator and/or seek emergency medical care if appropriate.

- **Grade 2:** stop infusion and treat symptoms following guidance in [Table 3](#). If symptoms resolve within two hours, the infusion may be restarted at 50% of the original infusion rate (e.g., from 100 mL/hr to 50 mL/hr).
- **Grade 3-4:** stop infusion and treat symptoms following guidance in [Table 3](#).

Table 3: Guidance for Management of Cytokine Release/Infusion Reaction Symptoms

Suspected Cytokine Release/Infusion-related Toxicity		Recommended Treatment

 Mild toxicity requiring symptomatic treatment only (e.g., fever, nausea, fatigue, headache, myalgia, malaise) 		
 Vigilant supportive care Maintain adequate hydration Antipyretics, non-steroidal anti-inflammatory drugs, antihistaminics, anti-emetics, analgesics as needed In case of mild symptoms persisting for > 48 hours assess for infections; empiric treatment of concurrent bacterial infections

 Symptoms or clinical findings requiring and responding to moderate intervention, such as: 
 O₂ requirement < 40% Hypotension responsive to fluids ± low dose of one vasopressor (e.g., < 50 mg/min phenylephrine) CTCAE Grade 2 organ toxicity 	
 No extensive co-morbidities 	
 All of the above Monitor cardiac and other organ functions closely

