3.7 Dose Modifications

Suspected adverse reactions (SAR) (for definition see [Section 6.1.2](#)) associated with APX005M and nivolumab exposure may represent an immunologic etiology. These AEs may occur shortly after the administration of investigational products or several months after the last dose of investigational product. Management of suspected adverse drug reactions may require treatment hold, dose reduction of APX005M, or discontinuation of one of both investigational products as per [Table 4](#). If a subject experiences several toxicities, the recommended dose modification should be based on the highest grade toxicity.

See [Section 3.4.1.2](#) for supportive care guidelines, including use of corticosteroids.

Table 4: Dose Modification Guidelines for Suspected Adverse Reactions

Toxicity	Grade	APX005M	Nivolumab
Neutropenia (± febrile)	3-4	Hold	Hold
Thrombocytopenia	3	Hold. Dose reduction if > 7 days	Hold
	4	Hold. Dose reduction	Hold. Discontinue if > 7 days
	3-4 with bleeding	Discontinue	Discontinue
Diarrhea/colitis	2	1 st occurrence: hold 2 nd occurrence: dose reduction	Hold
	3	1 st occurrence: dose reduction 2 nd occurrence: discontinue	Discontinue
	4	Discontinue	Discontinue
Uveitis, eye pain or blurred vision that does not improve to Grade 1 before next cycle	2-4	Hold	Discontinue
Increased bilirubin	2	Hold	Hold
	3-4	Discontinue	Discontinue
Increased AST, ALT	2	Hold	Hold
	3	Hold. Dose reduction For subjects with liver metastasis reduce dose only if Grade 3 > 72 hours	Discontinue
	4	Discontinue	Discontinue
Endocrinopathies	2	Hold	Hold
	3-4	1 st occurrence: Hold. Institute endocrine replacement therapy 2 nd occurrence: discontinue after consultation with Medical Monitor	1 st occurrence: Hold. Institute endocrine replacement therapy* 2 nd occurrence: discontinue after consultation with Medical Monitor
Nivolumab infusion reaction	2	Administer additional premedication. Increase infusion time to 90 min	1 st occurrence: continue 2 nd occurrence: discontinue
	3	Hold for 1 cycle. Continue single agent at following cycle	Discontinue
	4	Discontinue	Discontinue

Toxicity	Grade	APX005M	Nivolumab
APX005M infusion reaction/cytokine release syndrome	3	Hold. Dose reduction	Hold
	4	Discontinue	Discontinue
Pneumonitis	2	1st occurrence: hold 2nd occurrence: discontinue	1st occurrence: hold 2nd occurrence or if > 14 days: discontinue
	3-4	Discontinue	Discontinue
Creatinine elevation	2	Hold	Hold. Discontinue if > 7 days
	3	Hold	Hold. Discontinue if > 7 days

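### Sections 3.3.1 and 3.3.2 tell sites to restart an infusion after a reaction with no stated grade or time limit, which does not agree with Section 3.4.1.2 or Table 4

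*Protocol*

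**What the plan says.** **Administration sections.** Section 3.3.1 says "The nivolumab infusion can be interrupted in the case of infusion reaction (see", and the reference that follows is to Section 3.4.1.2. The next sentence reads "Once symptoms resolve, infusion should be restarted at 50% of the initial infusion rate", with 100 to 50 mL/hr as the example. Section 3.3.2 has the same pair of sentences for APX005M: "The APX005M infusion can be interrupted in the case of infusion reaction (see", again pointing to Section 3.4.1.2, then the restart instruction with 50 to 25 mL/hr as the example.

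**Supportive care.** Under infusion reaction/cytokine release, Section 3.4.1.2 tells the site at Grade 2 to stop and treat, and adds: "If symptoms resolve within two hours, the infusion may be restarted at 50% of the original infusion rate". The Grade 3-4 entry also says to stop and treat, and says nothing about restarting.

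**Dose modification.** Table 4 in Section 3.7 has two relevant blocks.
- "Nivolumab infusion reaction": at Grade 2, nivolumab continues after a first occurrence and is discontinued after a second. At Grade 3 and Grade 4 nivolumab is discontinued.
- "APX005M infusion reaction/cytokine release syndrome": at Grade 3, both products are held and APX005M is reduced. At Grade 4 both are discontinued. There is no Grade 2 row.

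The table footnote defines discontinuation as permanent, and a hold as lasting until the Section 3.6 retreatment criteria are met.

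**The concern.** The restart sentences in Section 3.3 are worded as what *should* happen, and symptom resolution is their only condition. The other two places attach grade, time and occurrence conditions. Someone who acts on the Section 3.3 sentence as written can restart an infusion that Section 3.4.1.2 does not provide for, or that Table 4 says must end permanently.

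The decision is made on the day, with the subject in the clinic, and concerns a toxicity that the protocol expects. Sites could handle the same event differently, and each could cite the protocol in support.

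**Working it through.** The point rests on no computed quantity. The only arithmetic in these passages is the halving of the infusion rate (100 to 50 and 50 to 25 mL/hr), and both examples are correct. The check is a comparison of the instructions, case by case.

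| Event, symptoms since resolved | 3.3.1 / 3.3.2 as worded | 3.4.1.2 | Table 4 |
|---|---|---|---|
| First Grade 2 nivolumab reaction, resolved within 2 h | Should restart | May restart | Nivolumab continues |
| Second Grade 2 nivolumab reaction, resolved within 2 h | Should restart | May restart | Nivolumab permanently discontinued |
| Grade 2 reaction to either product, resolved after 2 h | Should restart | No restart provision | Nivolumab reaction: by occurrence, as above. APX005M reaction: no row |
| Grade 3 nivolumab reaction | Should restart | Stop; no restart provision | Nivolumab permanently discontinued |
| Grade 3 APX005M reaction | Should restart | Stop; no restart provision | Both held; APX005M reduced |
| Grade 4 reaction to either product | Should restart | Stop; no restart provision | Both permanently discontinued |

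1. **Row 1** differs only in force (*should* against *may*).
2. **Row 2** sets Section 3.3.1 against Table 4. Section 3.4.1.2 says that its guidance does not replace the delays and modifications of Section 3.7, so Table 4 already prevails over Section 3.4.1.2 here. Nothing comparable ranks Section 3.3.1 below Table 4.
3. **Row 3** sets an instruction to restart against a provision whose two-hour condition has failed.
4. **Rows 4 and 6** are the clearest conflicts, because restarting cannot be squared with permanent discontinuation. For Grade 4, Section 4.1 also makes stopping mandatory where Section 3.7 discontinues both products.
5. **Row 5** is less direct on the Table 4 side. A hold runs to the Section 3.6 criteria, which are written for starting a new cycle. The same-day conflict is mainly with Section 3.4.1.2.

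**Does the cross-reference settle it?** In both administration sections it closes the sentence that permits interruption. The restart sentence follows separately, with its own condition (symptoms resolved) and its own verb. The reference leads to text that Section 3.4.1.2 describes as suggested measures, which need not be followed when the investigator judges the event unrelated. The order of precedence is stated between Sections 3.4.1.2 and 3.7, but not for Section 3.3.

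Two of these readings are inferences. *No grade or time limit* describes an unqualified sentence; the sections do not say that restart applies at every grade or after any delay. Likewise, Section 3.4.1.2 does not expressly forbid restart at Grade 3-4; it simply provides for none.

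**The case against.** The best defence is that the sections divide the work: Section 3.3 gives the restart rate, and Section 3.4.1.2 says when restart applies. The reference comes one sentence earlier, and the Grade 2 entry repeats both the 50% and the 100-to-50 mL/hr example. A careful reader could well take Section 3.4.1.2 as controlling. This stands as a plausible reading and lowers the severity. It does not remove the difference between *should* and *may*, and the text does not compel it.

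A reader might infer more than the documents support:

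- **Three competing instructions for a Grade 3 nivolumab reaction.** Stopping the infusion is the same-day action and discontinuation is the status afterwards, so those two agree. The Section 3.3.1 sentence is the one out of line.
- **A size taken from the single-agent study.** The Grade 3 and Grade 4 cytokine release events in Section 1.2.3 occurred at 1 mg/kg, and the Grade 3 event came in a later cycle. This study stops at 0.3 mg/kg, and Section 2.2.2 reports only Grade 2 or lower adverse reactions at the proposed doses, as a single agent. The frequency of Grade 3-4 reactions with the combination is not given.
- **A shift of one subject in three (33%) in the DLT rule.** Subjects who are not DLT-evaluable are replaced (Protocol Section 2.2; SAP Section 2.3.5), which restores the denominator. Non-laboratory Grade 4 non-hematologic toxicity attributed to the combination in the first cycle is a DLT under Section 3.5 whether or not the infusion restarts. Nivolumab is given once per 21-day cycle, so second Grade 2 reactions will mostly fall outside the DLT window.
- **That infusion staff work from Section 3.3.** The documents do not say so. They refer to a Pharmacy Manual that is not available here.

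**Conclusion.** The inconsistency is real and should be corrected. The restart sentences in Sections 3.3.1 and 3.3.2 carry no grade, time or occurrence limit, whereas Section 3.4.1.2 and Table 4 do, and the cross-reference does not clearly import those limits. The clearest conflicts are a Grade 3-4 nivolumab reaction, a Grade 4 APX005M reaction and a second Grade 2 nivolumab reaction, where Table 4 ends the product permanently.

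The weight of the point comes from the kind of decision affected. How many subjects it would touch cannot be estimated from the documents. No sample size, error rate, power figure or analysis definition changes, and an effect on the MTD is not demonstrated. The conclusion assumes that a site may read the restart sentence as standing on its own, which the wording allows but does not require.

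**What to change.** Reconcile the restart sentences in Sections 3.3.1 and 3.3.2 with Section 3.4.1.2 and Table 4, so that all four places give one consistent instruction for each situation in the comparison. State which section governs if they appear to differ; at present precedence is stated only between Sections 3.4.1.2 and 3.7. The content of the rule, including whether and when an infusion may be restarted, is the sponsor's medical decision, and none is proposed here.

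The cost is small: one sentence in each administration section, one line on precedence, and any matching wording in Section 3.4.1.2 or Table 4. If the Pharmacy Manual repeats the restart instruction, it should be brought into line. The SAP does not repeat the restart wording (its Section 2.3.4 describes only the planned infusions), so no SAP change, extra procedure or recalculation is needed.

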3.3.2 APX005M

APX005M is administered on Day 1 of each 3-week treatment cycle approximately 30 minutes following nivolumab using a 60 minute IV infusion. Sites should make every effort to target infusion timing to be as close to 60 minutes as possible. A window between -5 minutes and +10 minutes is permitted (i.e., infusion time is 55 minutes to 70 minutes).

The APX005M infusion can be interrupted in the case of infusion reaction (see [Section 3.4.1.2](#)). Once symptoms resolve, infusion should be restarted at 50% of the initial infusion rate (e.g., from 50 mL/hr to 25 mL/hr). A lower infusion rate may be considered for patients who experience repeated infusion reactions, after discussion with Apexigen Medical Monitor (or designee).

The Pharmacy Manual contains specific instructions for the preparation of the APX005M infusion and administration of infusion solution.

3.4 Concomitant Treatments

3.4.1.1 Premedication Prior to Administration of Investigational Product

All subjects should be premedicated approximately 30 minutes before the administration of first investigational product with a regimen containing:

- Oral H1 antagonist (e.g., loratadine 10 mg)
- Optional oral or IV H2 antagonist (e.g., ranitidine 150–300 mg, cimetidine 300–800 mg, nizatidine 150–300 mg, and famotidine 20–40 mg)
- Oral or IV nonsteroidal anti-inflammatory drug (may comprise ibuprofen 400 mg or equivalent)
- Oral or IV acetaminophen 500-650 mg.

When the time between premedication and scheduled APX005M administration exceeds 4 hours,

or if a subject experiences a Grade 2 infusion reaction to nivolumab, subjects may receive an additional course of premedication prior to APX005M administration.

